CSR	Clinical Study Report
DMC	Data Monitoring Committee
eCRF	electronic case report form
ELISA	enzyme-linked immunosorbent assay
CCI	CCI
FDA	Food and Drug Administration
FIX	coagulation factor IX
GGT	gamma-glutamyl transpeptidase
gc	gene copies
CCI	CCI
HBeAg	hepatitis B extracellular antigen

HBsAg	hepatitis B surface antigen
HBV DNA	hepatitis B virus deoxyribonucleic acid
HCV RNA	hepatitis C virus ribonucleic acid
CCI	CCI
hFIX	human coagulation factor IX
CCI	CCI
iCSR	interim Clinical Study Report
IFN γ	interferon gamma
IgG	immunoglobulin G
IgM	immunoglobulin M
IL-1 β	interleukin-1 beta
IL-2	interleukin-2
IL-6	interleukin-6
IMP	investigational medicinal product
INR	International Normalized Ratio
CCI	CCI
IU	international unit
IV	intravenous
LOD	limit of detection
MCP-1	monocyte chemotactic protein-1
MedDRA	Medical Dictionary for Regulatory Activities
NA	not applicable
NAB	neutralizing antibody
CCI	CCI
CCI	CCI
SAE	serious adverse event
SAP	Statistical Analysis Plan
SOC	System Organ Class

TEAE	treatment emergent adverse event
ULN	Upper Limit of Normal
US	United States
VAS	Visual Analogue Scale

Trademark Information

SAS

1. INTRODUCTION

This Statistical Analysis Plan (SAP) outlines the statistical methods for the display, summary and analysis of data for the uniQure Study CT-AMT-061-01. The SAP should be read in conjunction with the study protocol. This version of the SAP has been developed using the CT-AMT-061-01 Protocol (Version 3.0 dated 10 Feb 2021) and the CT-AMT-061-01 CRF (Revision 13.0 dated 02 Apr 2020).

2. STUDY OBJECTIVES AND ENDPOINTS

2.1 Study Objectives

The overall objective of CT-AMT-061-01 is to assess the efficacy of a single dose of 2×10^{13} gene copies (gc)/kg AMT-061 on the Factor IX (FIX) activity levels at six weeks after dosing in subjects with severe or moderately severe hemophilia B.

2.2 Study Objectives for CT-AMT-061-01

2.2.1 Primary Objective

To confirm that a single dose of 2×10^{13} gc/kg AMT-061 will result in FIX activity levels of $\geq 5\%$ at six weeks after dosing.

2.2.2 Secondary Objectives

- To assess effect of 2×10^{13} gc/kg AMT-061 on endogenous FIX activity at 52 weeks
- To assess effect of 2×10^{13} gc/kg AMT-061 on discontinuation of previous continuous prophylaxis
- To assess effect of 2×10^{13} gc/kg AMT-061 on total usage of FIX replacement therapy
- To assess effect of 2×10^{13} gc/kg AMT-061 on the annualized bleeding rate
- To assess effect of 2×10^{13} gc/kg AMT-061 on specific types of bleeding events (e.g. spontaneous bleeds, joint bleeds, and traumatic bleeds).

2.2.3

CCI

CCI

CCI

2.2.4 Safety Objectives

The safety objectives include monitoring the following:

- Adverse Events (AE)
- Formation of anti-AAV5 antibodies (total immunoglobulin M and immunoglobulin G [IgM and IgG], neutralizing antibodies)
- AAV5 capsid-specific T cell response
- Formation of anti-FIX antibodies
- Formation of FIX inhibitors
- Hematology and serum chemistry results
- Shedding of vector DNA in blood and semen
- Inflammatory markers
- Aspartate aminotransferase (AST) / Alanine aminotransferase (ALT) elevations
- Use of corticosteroids required to preserve FIX activity in the context of AST/ALT elevations
- Abdominal ultrasound
- Alpha-fetoprotein (AFP)

2.3 Study Endpoints for CT-AMT-061-01

2.3.1 Efficacy Endpoints

2.3.1.1 Primary Efficacy Endpoint

- FIX activity level at Week 6 post AMT-061 dose.

[figure not shown]
2.3.1.2 Secondary Efficacy Endpoints

- Endogenous FIX activity level at Week 6 and Week 52 post AMT-061 dose
- Remaining free of previous continuous prophylaxis during 52 weeks following AMT-061 dosing
- Total usage of FIX replacement therapy until 52 weeks following AMT-061 dosing, excluding ad hoc prophylaxis for invasive procedures
- Annualized bleeding rate after 52 weeks of AMT-061 dosing (including a further breakdown of the frequency and percentage of spontaneous, traumatic, and joint bleeding events)

2.3.1.3

CCI

CCI

2.3.2 Safety Endpoints

Secondary safety endpoints include the following:

- AEs
- Hematology and serum chemistry parameters
- ALT/AST levels and corticosteroid use for ALT/AST elevations
- Parameters on antibody formation to AAV5 and hFIX
- AAV5 capsid-specific T cell response
- Inflammatory markers
- Vector DNA in semen and blood
- AFP

Safety endpoints are observed over the 52-week post-treatment follow-up phase and for an additional four years in the long-term follow-up phase. An additional endpoint in the long-term follow-up is abnormal findings on the abdominal ultrasound assessment. Please refer to protocol for more details.

3. STUDY DESIGN AND ANALYTICAL CONSIDERATIONS

3.1 Study Design

3.1.1 Overall Study Design and Plan

CT-AMT-061-01 study is a phase IIb, open-label, single-dose, single-arm, multi-center study to confirm the FIX activity in response to 2×10^{13} gc/kg AMT-061 administered to adult subjects with severe or moderately severe hemophilia B. There will be a screening phase, a treatment and post-treatment follow-up phase, and a long-term follow-up phase.

This study will be conducted at approximately 3 sites, for a minimum of 3 subjects. Subject eligibility according to the trial in- and exclusion criteria will be evaluated at Screening and during the period up to baseline (Day 0 pre-IMP) in the CT-AMT-061-01 study.

[figure not shown]
After a maximally six-week screening period, eligible subjects will receive a single intravenous dose of 2×10^{13} gc/kg AMT-061. After dosing, the subject will be followed for a total of five years (60 months). The post-dose follow-up visits are planned as follows:

- Weekly up to Week 12
- Every second week from Week 12 to Week 26
- Every month from Week 26 to Week 52
- Every half year from Week 52 to Month 60

All subjects will be monitored for 24 hours (overnight stay) after dosing. Dosing of subjects will be separated by a minimum of 14 calendar days to allow for subject safety monitoring of tolerance to the IMP, detection of AEs, and to ensure appropriate action can be taken in case any acute reactions arise.

The overall study design is summarized and illustrated in Figure 1.

Figure 1 Study Scheme

In CT-AMT-061-01, subjects who withdraw prior to IMP administration or within the first six weeks after IMP administration will be replaced. Subjects who discontinue after six weeks post IMP administration will not be replaced.

If a subject discontinues due to being lost to follow-up, then three documented attempts must be made to contact the subject lost to follow-up at any time point prior to the last scheduled contact (office visit or telephone contact).

An interim analysis will be performed after Week 6 post-dose to determine the effect of AMT-061 on FIX activity.

After Week 52 post-dose, efficacy and safety data will be collected on all subjects. These subjects will be followed for another four years for evaluation of efficacy parameters and safety. Please refer to the protocol for more information.

3.1.2 Prior and Concomitant Medications

For the definition of prior medication/therapy, refer to [Section 5.6.1 of the protocol](#). For the definition of concomitant medication/therapy, refer to [Section 5.6.2 of the protocol](#). For operational definitions and detail, see [Appendix 1, Data Handling Rules](#) [under the category of “Prior and concomitant medication/treatment”].

3.2 Interim and Final Analyses

After six weeks post-dose, an interim analysis for efficacy will be done using the available data on FIX activity. Safety data will also be evaluated. The results will be reported in an interim Clinical Study Report (iCSR).

After 52-weeks post-dose, efficacy and safety data will be collected on all subjects. The data will be locked, analyzed, and reported in a Clinical Study Report (CSR).

After 2.5-years post-dose, efficacy and safety data will be collected on all subjects. The data will be locked, analyzed, and reported in a Clinical Study Report (CSR) addendum.

After 60-months post-dose, efficacy and safety data will be collected on all subjects. The data will be locked, analyzed, and reported in a CSR Addendum.

3.3 Sample Size

No formal sample size calculation is required for this trial. From a clinical perspective, a minimum of three subjects are considered sufficient to provide a reliable impression of the FIX activity levels and safety profile that will be demonstrated with a single dose of 2×10^{13} gc/kg AMT-061 at Week 6 post-dose. Additional subjects may be added based on the 6-week results and either DMC review or sponsor recommendation. Further information is available in the DMC Charter.

4. DATA AND ANALYTICAL QUALITY ASSURANCE

The overall quality assurance procedures for the study data, statistical programming and analyses are described in Standard Operating Procedures (SOPs) of Everest Clinical Research. Detailed data management procedures are documented in the study Data Management Plan, Data Validation Check Specifications, and Integrated Safety Data Review Plan.

5. ANALYSIS POPULATIONS

5.1 Population Definitions

Study CT-AMT-061-01 subjects will consist of adult males with severe or moderately severe hemophilia B. Considering the small sample size (N=3), no analysis population will be defined. No formal statistical analyses will be performed – only descriptive statistics and plots. All available data on treated subjects will be included in all presentations.

6. STATISTICAL ANALYSIS

6.1 Statistical Analysis

No formal, inferential statistical analyses will be performed considering the small sample size used in Study CT-AMT-061-01.

All available data will be presented in plots, tabular displays, and listings to visualize individual effects for selected efficacy and safety measures. If applicable, continuous variables will be summarized with descriptive statistics including: the number of non-missing values, mean, standard deviation, median, minimum, and maximum. In some cases, the standard error of the mean and/or confidence intervals will be presented. Categorical variables will be summarized by number, percent of patients and, if applicable, the number of events.

The planned interim analysis at Week 6 is described in Section 6.2. The statistical analyses for the main CSR (at Month 12) and the 2.5-year CSR are described in [Sections 6.3, 6.4, 6.5, 6.6, 6.7, and 6.8](#). The analyses for the 12-month CSR followed the SAP text (version 1.0, 06 Aug 2018) as it existed at the time of the 12-month analysis. Any revisions to the SAP text that have been made since that time are to be applied to the 2.5-year CSR. The statistical analyses for the 60-month CSR Addendum are described in [Section 6.9](#).

If for any reason additional dose groups (cohorts) of subjects are added to the study, then analyses will be performed separately by cohort.

6.2 Planned Interim Analysis

Six weeks after administration of AMT-061, a data-cleaning round will be performed to provide data for one interim analysis for efficacy using the available data on the primary efficacy parameter - FIX activity. The primary efficacy endpoint will be reported as detailed in [Section 6.7.1](#). FIX activity will be summarized (and listed) by visit, overall and by patient, over the 6-week period since administration of AMT-061. By-subject plots of FIX activity over time will be overlaid with plots of exogenous FIX consumption (time of administration) and with the times of occurrence of bleeding events over the first 6 weeks subsequent to AMT-061 administration.

The ratio of FIX activity (%) to FIX protein (%) will be tabulated. A table will also be provided to summarize the FIX activity (%) by patients with or without pre-existing neutralizing antibodies to FIX. A scatter plot of FIX activity (%) by baseline titer of neutralizing antibodies to

AAV5 will also be presented to show the correlation of baseline titer of neutralizing antibodies to AAV5 and FIX activity at Week 6.

Treated bleeding episodes and annualized treated bleeding rates during the post prophylaxis period (as defined in [Section 6.7.2](#)) will be tabulated by the following bleed types: all bleeds, spontaneous, traumatic, medical/dental, and other.

The annualized dose of Factor IX replacement during the post IMP period and the actual exogenous Factor IX use overall and by patient will be tabulated.

The incidence of treatment-emergent adverse events, serious adverse events, TEAEs in descending frequency, related adverse events, and related serious adverse events will be tabulated.

Additional figures showing ALT/AST Levels (U/L) and corticosteroid use for ALT/AST elevations over time, T-cell (AAV5-capsid) ELISPOT ((SFC)/million PBMCs) over time, and inflammatory markers over time will be produced. Subject disposition and demographic data will be listed for all subjects screened and all subjects treated. Baseline characteristics will be listed and will include the following: hemophilia B history, joint status at screening, bleeding history in the year prior to screening, history of previous FIX replacement therapy use, prior medication/therapy, medical and surgical history, and FIX gene sequencing.

Additional efficacy endpoints will be listed and include the following: FIX protein concentration (%).

Safety listings will include the following: Treatment-emergent adverse events, serious adverse events, TEAEs of special notification, potentially clinically significant (PCS) laboratory values, PCS vital signs, other laboratory values, vector shedding, and inflammatory markers.

Table, listing, and figure shells for the 6-week interim analysis can be found in [Appendix 4 of the DMC Charter](#).

The results will be reported in an interim Clinical Study Report (iCSR).

6.3 Data Handling Rules and Definitions, Including Handling of Missing Data

Missing data will be maintained as missing in the safety and efficacy datasets, unless specified otherwise.

Data for Adverse Events Summaries by Severity and Relationship to Study Drug

For the AE summaries by severity (mild, moderate, or severe), an AE with missing severity will be deemed as severe. For the AE summaries by relationship to study drug, an AE with a missing relationship to study drug will be deemed as definitely related. Seriousness cannot be imputed as 'Yes' by default, since this would affect the reconciliation between trial database and registry of SAEs.

Data for Laboratory and Vital Sign Summaries (Continuous Parameters)

Data from unscheduled visits will not be used for by-visit summaries (unless they were assigned to a scheduled visit based on the use of an analysis window as given in [Section 6.3](#) under the subsection “[Time Windows for Statistical Analysis](#)”). Data from both scheduled and unscheduled visits will be used for determining incidence of clinically significant values.

Data for All Laboratory Summaries

For safety laboratory values, laboratory values of ‘>=x’ or ‘<=x’ will be taken as the value of x in the analyses. If a laboratory value is prefixed with ‘>’: the available original value +0.001 will be used for table summaries; if a laboratory value is prefixed with ‘<’, then the original value – 0.001 will be used in table summaries.

Study Day and Day of Assessment or Event

Study Day and Day of Assessment or Event definitions are provided in [Appendix 1, Data Handling Rules](#).

Time Windows for Statistical Analysis (to be applied in case of missing scheduled-visit data):

Scheduling difficulties due to the coronavirus disease (COVID-19) pandemic may result in an increased number of missed, delayed, or unscheduled visits. Scheduling difficulties may also result in the performance of assessments at a scheduled visit where performance of the assessment was not originally planned. As an action to mitigate risk, analysis windows will utilize such unplanned assessments as follows. A schema for the assignment of such unplanned assessments to scheduled time points for visit-based endpoint analysis and summary (for visit-based efficacy and safety endpoints) will be defined as follows:

- An unplanned assessment will be assigned to a scheduled visit only if that visit has a missing value for the relevant endpoint and the visit was a scheduled time point for the performance of the assessment per the study protocol.
- Analysis windows for the assignment of unplanned assessments will range from the previous visit at which the endpoint is planned to be collected to the next visit at which the endpoint is planned to be collected.
- The unplanned assessment closest in time within the analysis window (either before or after) will be used to replace a missing assessment for a scheduled visit. If two unplanned

assessments are both the closest in time, with one being before and the other being after, the earlier assessment will be used.

- For visit-based efficacy endpoints, values obtained before the post prophylaxis period will not be candidates to be used for imputing missing values for post-treatment visits that are during the post prophylaxis period.
- For all visit-based endpoints, values obtained prior to treatment will not be used for imputing missing values for post-treatment-period planned assessments.
- Only values from unplanned assessments (not planned assessments) will be used to replace a missing scheduled assessment.
- An unplanned assessment may be used more than once provided it lie within the analysis window for two consecutive scheduled time points at which the assessment was not performed as planned.

For factor IX activity and factor IX protein, only central-laboratory unplanned-assessment values will be candidates for assignment to a scheduled visit that has no central-laboratory value.

An exception to the above windowing rules is that Vital Signs will have values assigned to analysis visits according to the visit windows given in Table 6 (Analysis Study Time Windows for Vital Signs Assessments).

Any other rules for missing data handling will be given in the endpoint-specific sections.

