6.1.4 Long-term Follow-up

Subjects will visit the clinic every 26 weeks (6 months \pm 2 weeks). During these visits, it is recommended that the subject completes the CCI (only at Month 24, 36, 48, and 60), prior to any other trial procedure is performed. Further, a physical examination, evaluation of the CCI (only at Month 24, 36, 48, and 60), sampling for efficacy and safety laboratory parameters, and review of AEs and concomitant medications will be performed. An abdominal ultrasound will be performed at the Month 30, 36, 42, 48, 54, and 60 visits. In addition to AE review during these visits, there should be an additional contact moment between site staff and subject in between these routine visits to facilitate at least quarterly monitoring of occurrence of AEs. Options for how visits may occur to accommodate safety concerns and restrictions due to COVID-19 are described in Section 3.1.1.

In the long-term follow-up phase, subjects will document their use of factor IX replacement therapy and bleeding episodes in study-specific paper diaries. Subjects are expected to bring their long-term follow-up bleed diaries and long-term follow-up factor IX use diaries to every study visit during the long-term follow-up phase. At each visit, site staff will collect the information that is new since the previous visit in the paper diaries. In between study visits, subjects should contact the site staff immediately in case of an experienced bleed and/or factor IX use in addition to completing the questions/information requested on the paper diaries to capture all information.

In total, each subject will be followed for five years after administration of AMT-061. This is in line with the European Medicines Agency (EMA) guideline on follow-up of subjects administered with a gene therapy medicinal product (EMA/CHMP/GTWP/60436/2007) and the Food and Drug Administration (FDA) guidance on long-term follow-up after administration of human gene therapy products.

At the end of the long-term follow-up all end-of-trial procedures, i.e., the Month 60 procedures, as detailed in Table 3 and Table 4, should be taken. At the end of the trial, all safety and efficacy data will be reported in a CSR addendum (5-year analysis).

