6.7.1 Primary Efficacy Endpoint

The primary efficacy endpoint is the FIX activity level at Week 6 post dose. If FIX replacement therapy was used within 10 days of the Week 6 post-dose time point, the Week 8 post-dose FIX activity level will be used. If FIX activity is still contaminated, then the Week 10 post-dose FIX activity level will be used, etc. This would result in a corresponding postponement of the nominally Week-6 interim efficacy analysis.

FIX activity levels will be presented in % of normal units. Descriptive statistics (across visits) including the mean, standard deviation, median, minimum, and maximum will be presented at six weeks after dosing by subject. Such descriptive statistics will also be displayed by visit across subjects.

The Week 6 primary analysis of FIX Activity will proceed as follows. FIX activity will be summarized (and listed) by visit over the 6-week period since administration of AMT-061. By-subject plots of FIX activity over time will be overlaid with plots of exogenous FIX consumption (start and end times) and with the times of occurrence of bleeding events over the first 6 weeks subsequent to AMT-061 administration.

Plots of FIX activity levels over time per subject will be presented. Descriptive statistics and plots will display uncontaminated results only, i.e. FIX activity levels that are not affected by exogenous FIX use during the trial. Alternatively, the by-subject FIX activity plots may display the time of exogenous FIX use instead of altogether omitting the contaminated FIX results. The required wash out period (in order to consider a FIX activity level to be “unaffected” – i.e. “uncontaminated”) will be 10 days. FIX activity level over six weeks after dosing (by subject) will also be listed and will include a flag for contaminated results. These analyses will be presented in the Week 6 iCSR.

The above-mentioned set of analyses – being done for the Week 6 CSR will also be carried out for the Week 52 main CSR (and 2.5 Years CSR), but over the time period of 52 Weeks (and 2.5 Years) instead of over 6 weeks.

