6.7.2 Secondary Efficacy Endpoints

FIX activity over 52 weeks (and 2.5 years) (post IMP administration), annualized FIX consumption, Prophylaxis FIX replacement therapy use over 52 weeks (and 2.5 years), and on-demand FIX replacement therapy use over 52 weeks (and 2.5 years) will be presented using descriptive statistics across subjects for each visit and across time for each subject.

Bleeding episodes and annualized bleeding rates in the post-prophylaxis period and type (spontaneous bleeds, joint bleeds, and traumatic bleeds) will also be presented using descriptive statistics. All events that are emergent during the period will be counted.

The end of continuous prophylaxis requires 3 events: (1) study drug was administered, (2) uncontaminated factor IX activity (post-study drug) has since been observed to be $\geq 5\%$, and (3) the subject has not used exogenous factor IX for some contiguous time period of at least 15 days after study drug administration. The tenth day of the first 15-day contiguous period where these criteria are met is then taken as the end of prophylaxis. The Post-Continuous-Prophylaxis period begins on the day after the end of continuous prophylaxis. If the field for whether the bleed was treated is missing, then (for conservativeness) it will be assumed that the bleed was treated with factor IX. If the assessment field for newness of the bleed is missing, then (for conservativeness) it will be assumed that the bleed is new. If the assessment field for trueness of the bleed is missing, then (for conservativeness) it will be assumed that the bleed is true. A supplemental analysis will count only bleeds that were treated with exogenous factor IX. A supplemental analysis will count only bleeds that are assessed by the investigator to be new and true bleeds (per entry on the CRF).

[figure not shown]
In the analysis (from the 2.5-year data cut henceforth), any person-time during the post-treatment period within 5 half-lives subsequent to exogenous factor IX use will not be counted in the time at risk of (having) a bleeding event. Both the date and time of the exogenous factor IX injection start will be taken into account to identify time periods to be excluded. Nevertheless, any bleeds occurring during the post-prophylaxis period should still be counted as events, even if they

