6.8.2 Changes in Abdominal Ultrasound

To monitor subjects for liver fibrosis and potential occurrences of liver malignancies, abdominal ultrasound assessments will be performed. These ultrasound assessments will occur every 6 months beginning with the Month 30 Post-Treatment Visit.

A table will be used to summarize normal and abnormal results at each visit. All abdominal ultrasound data will be listed.

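### SAP 6.3 lets one unplanned ultrasound scan count as the result at two consecutive missed visits in Table 3.7.1, with neither shown as missing (minor)

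*SAP*

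**What the plan says.** - **Substitution rule (SAP 6.3, time windows for statistical analysis).** A missing scheduled value for a visit-based efficacy or safety endpoint is replaced by the closest unplanned assessment. The window "will range from the previous visit at which the endpoint is planned to be collected to the next visit" planned for that endpoint. No tighter maximum distance is given.
- **Reuse (same section).** "An unplanned assessment may be used more than once provided it lie within the analysis window for two consecutive scheduled time points" at which the planned assessment was not performed. Vital signs are the only endpoint taken out of these rules; they have their own windows in SAP Table 6.
- **Ultrasound (SAP 2.3.2 and 6.8.2).** Abnormal ultrasound findings are a named endpoint of long-term follow-up. "These ultrasound assessments will occur every 6 months beginning with the Month 30 Post-Treatment Visit". A table summarises normal and abnormal results at each visit, and all ultrasound data are listed.
- **Visit spacing (Protocol 6.1.4).** "Subjects will visit the clinic every 26 weeks", that is, every 6 months. Protocol Table 3 also allows an ultrasound at an additional visit, so an unplanned scan can occur.
- **Table 3.7.1 shell (SAP Appendix 5).** For each visit it gives Normal and Abnormal as n/N1, where N1 counts subjects with a non-missing result, and it has a Missing column. Its footnote does not mention substituted or reused scans.

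**The concern.** The six-monthly scans are there to detect liver fibrosis and malignancy (Protocol 6.2.3.4). Table 3.7.1 is where a reader would check whether each subject was scanned at each visit and what was found, and its Missing column is there to show gaps. Under the reuse rule, one scan can put a result in two rows and remove both gaps. The table would then report one more visit of liver surveillance than took place, whether the repeated result is normal or abnormal. The default in SAP 6.3 is that missing data stay missing unless otherwise specified. Here the exception produces a wrong count in a table built to show missingness.

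**Working it through.** **Inputs.** Three subjects (SAP 5.1). Scans planned at Months 30, 36, 42, 48, 54 and 60 (Protocol Table 3). Spacing of 26 weeks (Protocol 6.1.4). Window and reuse rule from SAP 6.3. The plan gives no figure of its own to reproduce.

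**1. Where a reused scan must lie.** The window for Month 36 runs from Month 30 to Month 42. The window for Month 42 runs from Month 36 to Month 48. They overlap only from Month 36 to Month 42, so a scan used for both visits lies between them.

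**2. Distance from target.** For a scan x weeks after Month 36, the distances to the two targets are x and 26 − x. They sum to 26, so the larger is at least 26/2 = 13 weeks.

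| x (weeks) | to Month 36 | to Month 42 | larger |
|---|---|---|---|
| 13 | 13 | 13 | 13 |
| 6.5 | 6.5 | 19.5 | 19.5 |
| 1 | 1 | 25 | 25 |

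Calendar gaps of 6 months run from 181 to 184 days, which puts the minimum at 91 to 92 days (13.0 to 13.1 weeks). The bound does not depend on how months are counted.

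**3. Effect on Table 3.7.1.** Suppose two subjects are scanned at both visits, and the third misses both but has one unplanned scan at Month 39. Actual scans: 2 × 2 + 1 = 5.

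| | Month 36 N1 | Month 36 Missing | Month 42 N1 | Month 42 Missing | Results shown |
|---|---|---|---|---|---|
| SAP 6.3 as written | 3 | 0 | 3 | 0 | 6 from 5 scans |
| Each scan used once | 2 | 1 | 3 | 0 | 5 from 5 scans |

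Month 39 is equidistant from the two visits. The second line assigns the scan to the later one.

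**4. Which report.** The 2.5-year report ends at Month 30, the first planned scan. Two ultrasound rows filled from one scan can therefore arise only in the Month 60 addendum, which repeats the same analyses on 60 months of data (SAP 6.9).

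**5. Should the same restriction apply to factor IX means?** Assume a steady fall of s points per 26 weeks; the documents give no rate for this product. A reused value shifts the three-subject mean by (x/26)s/3 at one visit and (1 − x/26)s/3 at the other, in opposite directions. The sizes sum to s/3, which is 0, 0.33, 0.67 or 1.33 points for s = 0, 1, 2 or 4.

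The alternative is to leave that subject out of a visit. Assume subjects at 18, 40 and 76%, the predicted range and mean in Protocol 1.3.1. The mean is (18 + 40 + 76)/3 = 44.7. Without the first, second or third subject it becomes:
- (40 + 76)/2 = 58.0, a shift of +13.3
- (18 + 76)/2 = 47.0, a shift of +2.3
- (18 + 40)/2 = 29.0, a shift of −15.7

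On these assumptions the shift from omission (2.3 to 15.7 points) exceeds the largest displacement error (1.33 points). A count table with a Missing column faces no such trade-off.

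**The case against.** The strongest defence is that the rule is open, reasoned and guarded. SAP 6.3 gives pandemic scheduling as its reason. It allows only unplanned values to substitute, takes the nearest, bars pre-treatment values from post-treatment visits, and requires central-laboratory values for factor IX. The triggering case is rare: two consecutive half-yearly scans must be missed and an unplanned one must fall between them. Protocol 3.1.1 offers several ways to keep visits going.

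The case can also be traced. All ultrasound data are listed, Listing 4.1.3 covers missed visits, the eCRF records missed visits and reasons (Protocol 8.2), and the reports summarise the impact of COVID-19 (Protocol 9.3). Clinically significant ultrasound abnormalities are recorded as adverse events (Protocol 6.2.3.4). The trial is descriptive throughout.

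All of that stands, and it keeps the point minor. It does not answer the count in Table 3.7.1. The pandemic reason supports using an unplanned scan once; it does not explain letting the same scan close two gaps.

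A reader might go further and infer that reuse should be struck out for every endpoint. The documents do not support that. Step 5 shows that omission can cost more than displacement for factor IX means, and the displacement error is zero if expression is stable, as Protocol 1.3.2.2 reports for the precursor vector. For laboratory safety, the count of notable values does not depend on windowing: "Data from both scheduled and unscheduled visits will be used for determining incidence of clinically significant values".

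A reader might also infer double counting within a subject, because factor IX activity is "presented using descriptive statistics across subjects for each visit and across time for each subject" (SAP 6.7.2). The SAP does not say that the across-time summaries use substituted values. If they did, then with Months 18 and 24 filled from one Month 21 sample, the Week 52 to Month 30 mean would be unchanged and the SD would be 1.22s instead of 1.29s.

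**Conclusion.** The point holds for abdominal ultrasound and is minor. Followed as written, SAP 6.3 can make Table 3.7.1 show one scan as results at two visits with Missing=0 at both, and at least one of those rows is 13 weeks or more from the scan. The 13-week bound follows from the 26-week spacing and the stated windows and needs no further assumption. The 5-for-6 count assumes that one of three subjects misses two consecutive scans and has one unplanned scan between them.

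Three further readings are not supported:
- **Breach of the protocol's visit windows.** Those windows, including the one-month allowance either side for ultrasounds affected by COVID-19, govern when scans are done, not how they are tabulated.
- **No marking anywhere.** The efficacy shells are redacted and the listing shells were removed, so nothing can be said about flags there. The visible laboratory shell, Table 3.2.1, implies that some unscheduled values are assigned to visits, though not which ones.
- **Effect on the primary result.** Week 6 factor IX is not affected, and neither is the original 52-week report, which followed the SAP version then in force (SAP 6.1).

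**What to change.** 1. In SAP 6.3, exempt abdominal ultrasound from the reuse bullet. Each unplanned scan fills at most one missing visit, the nearest; if it is equidistant, the later one. The other visit counts as Missing. The tie rule is needed because the existing one covers two unplanned values equally close to one visit, not one value midway between two visits.
2. Add a footnote to Table 3.7.1 giving the number of substituted scans and their actual study days.
3. Keep the current rule for factor IX and laboratory by-visit means. Add a footnote to those tables stating how many values were substituted and how many were used twice.

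The cost is one sentence of SAP text and the table footnotes. The downside is that, when the case arises, one more ultrasound cell is shown as missing, which is what happened at that visit.
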